5.6.1 Primary endpoint

The primary efficacy endpoint is based on the blinded raters' Clinical Impression of Change in Severity (CI-CS) score over 6 weeks determined by comparing videos showing the patient's performance on a pre-defined anchor clinical symptom scale: either the 9 Hole Peg Test of the Dominant Hand (9HPT-D) or the 8 Meter Walk Test (8MWT).

For each patient, there will be two CI-CS scores. These two scores indicate the level of change in severity observed in Visit 4 (end of treatment) compared to Visit 2 (baseline) and the level of change in severity observed in Visit 6 (end of washout) compared to Visit 4 (end of treatment). Both CI-CS scores are measured on a 7-point Likert-point scale (-3 = *significantly worse* to +3 = *significantly improved*, see Section 5.2 for the precise definition) and the primary endpoint is defined as the difference between both CI-CS scores.

The primary endpoint will be summarized using descriptive statistics, including a frequency table, and frequency percentages will be presented graphically using a bar chart.

The primary statistical analysis will be performed using a one-sample t-test comparing the CI-CS difference score to zero. Statistical output will present the number of patients included in the analysis, both CI-CS scores, the mean of the difference, the corresponding two-sided 90% confidence interval, and a one-sided p-value.

The assumption of normality will be visually checked and if the assumption does not hold, a Wilcoxon signed-rank test will be performed instead of the t-test using the difference score. Statistical output will then present the number of patients included in the analysis, both CI-CS scores, the (pseudo-) median of the difference using the Hodges-Lehmann estimator, the corresponding two-sided 90% confidence interval, and a one-sided p-value.

5.6.2 Key secondary endpoints

All key secondary endpoints will be presented using the mITT and PPS populations.

Clinical Impression of Change in Severity

The CI-CS scores on the pre-defined anchor test for Visit 4 versus Visit 2, and the CI-CS score on the pre-defined anchor test for Visit 6 versus Visit 4 will be evaluated separately. These key secondary endpoints will be summarized using descriptive statistics and frequency tables, and percentages will be shown graphically using a bar chart. No sensitivity analysis will be applied.

Change in severity score based on Averaged Clinical Impression of Severity (CI-S)

CI-S scores are measured on a 7-point Likert-point scale (-3 = *among the most extremely ill patients* to +3 = *normal, not at all ill*; see Section 5.2 for the precise definition) and the primary endpoint is defined as the difference between both CI-CS scores.

Improvement in the pre-defined anchor test measure will be evaluated based on the change in the blinded raters' CI-S scores between the baseline period (average for Visit 1 and Visit 2) and end of treatment period (average for Visit 3 and Visit 4) minus the change in CI-S between end of treatment period (average for Visit 3 and Visit 4) and end of washout period (average for Visit 5 and Visit 6). Note that if a CI-S score is missing at one visit for a period, but available at the other visit in the same period, that one value will be used instead of the average. The presentations and statistical analyses will be similar to the primary endpoint, excluding the sensitivity analysis which is only to be used for the primary endpoint. Data received for non-anchor CI-S scores will only be listed.

Clinical Impression of Change in Severity reclassified on a 3-point scale

Using the CI-CS outcome on the pre-defined anchor test based on the data for Visits 2 and Visit 4, any patient given a score <0 on the CI-CS will be classified as worsened (-1). Any patient classified as 0 on the CI-CS will be classified no change (0). Any patient given a score

>0 on the CI-CS will be classified as improved (+1). Similarly, the CI-CS comparing Visit 4 and Visit 6 will be reclassified and the differences between these two scores on a 3-point scale will be calculated.

The descriptive table and graphical presentations will be similar to the primary endpoint. No statistical analysis will be performed, and no sensitivity analysis will be applied.

Clinical Impression of Change in Severity (CI-CS) score non-primary anchor test

Descriptive statistics and frequency tables of the CI-CS scores for the test (9HPT-D or 8MWT) that was not selected as the primary anchor test will be presented for Visit 4 versus Visit 2, and separately, for Visit 6 versus Visit 4. No plots will be created, and no sensitivity analysis will be applied.

5.6.3 Additional secondary endpoints

All additional secondary endpoints will be presented using the mITT and PPS populations, and all individual data will be listed as well. No sensitivity analysis will be applied.

Measurement of Ataxia and Functioning

- SARA total score
- SCAFI total score
 - 9HPT-D
 - 9HPT-ND
 - 8MWT
 - PATA test

Descriptive statistics will be used to summarize the endpoints above at each visit.

The subscores of the SARA score (gait, stance, sitting, speech disturbance, finger chase, nose-finger test, fast alternating hand movements, heel-shin slide) will also be summarized for each visit using descriptive statistics. Stacked bar charts will be provided per visit, based on the subscores of the total SARA score.

Spaghetti plots of individual patient SARA total scores and the SCAFI total scores versus time will be made as well as a mean or median display versus time, depending upon the distribution, and corresponding two-sided 90% CI at each visit.

The average SCAFI subscores (8MW_avg, 9HPT-D_avg, 9HPT-ND_avg and PATA_avg) as determined according to Section 10.1, following the scoring manual, will also be summarized with descriptive statistics.

The changes in SARA total score, SCAFI total score, the SCAFI subscores (8MW_avg, 9HPT-D_avg, and PATA_avg) between Visit 2 and Visit 4, as well as the changes between Visit 4 and Visit 6 will be analysed using a one-sample t-test or a Wilcoxon Signed Rank test depending on the distribution of the data. The SCAFI subscore 9HPT-ND_avg will only be descriptively summarized in tabular format.

Measurement of Health-related Quality of Life

The results of EQ-5D-5L as well as the EQ-5D-Y will be combined into a 5-digit number presenting the health status of the subject. Frequency tables will be presented per visit for the 5 domains, as well as for the 5-digit number of the EQ-5D-5L and the EQ-5D-Y separately.

In addition, EQ-5D-5L and EQ-5D-Y domain percentages will be presented in separate bar charts per visit, with all visits combined into one plot (if possible).

The EQ-VAS score will be summarized by visit using descriptive statistics for patients aged < and \geq 18 years combined. Spaghetti plots of individual patient EQ-VAS scores versus time will be made as well as a mean or median display versus time, depending upon the distribution, and corresponding two-sided 90% CI at each visit.

Measurement of Overall Neurological Status

The mDRS composite score and individual components (ambulation, language, manipulation, swallowing, seizures, and ocular movement) will be summarized using descriptive statistics at each visit. As graphical display, a stacked bar chart of the 6 mDRS subscores at each visit will be created. Spaghetti plots of individual patient mDRS composite scores versus time will be made as well as a mean or median display versus time, depending upon the distribution, and corresponding two-sided 90% CI at each visit.

Furthermore, changes in the mDRS composite score between Visit 2 and Visit 4 as well as between Visit 4 and Visit 6 will be descriptively presented in a summary table.

Measurement of Global Impression

The three CGI-S scores (scored by treating physician, caregiver, and patient) will be summarized using descriptive statistics and frequency tables for each visit.

Bar charts will be presented for the three CGI-S scores, spaghetti plots of individual CGI-S scores versus time will be made as well as a mean or median display versus time, depending upon the distribution, and corresponding two-sided 90% CI at each visit.

Descriptive statistics and frequency tables will also be used to summarize the three CGI-C scores (treating physician, caregiver and patient) between Visit 2 and Visit 4, and between Visit 4 and Visit 6, and corresponding bar charts will be created.

The CGI-C scores for Visit 4 versus Visit 2, and for Visit 6 versus Visit 4 will be evaluated using descriptive statistics. Similarly, the CGI-C from Visit 2 to Visit 4 minus the CGI-C from Visit 4 to Visit 6 will be presented descriptively. In addition, the CGI-C measures for treating physician will be analyzed similar to the primary endpoint: the CGI-C from Visit 2 to Visit 4 minus the CGI-C from Visit 4 to Visit 6 will be compared to a difference of zero using a one-sample t-test or Wilcoxon signed-rank test.

Note that CGI-C is referred to as CGI-I in the eCRF.

It is important to realize that the CGI-S and CGI-C scores per visit for each patient as provided by the caregiver may be based on varying caregivers and hence additional variation is introduced. No correction for this variation can be done and a footnote will be added to the table to describe this situation.

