Each video pairing (CI-CS) will be read by the two independent raters, and the appropriate Likert scale score will be entered onto the eCRF. If there is a difference of one (1) point in the two primary blinded reviewers' CI-CS scores for a specific video pairing, the two scores will be averaged. If there is difference greater than one (1) point between the two primary blinded reviewers' CI-CS scores for a specific video pairing, an adjudication read will be triggered. In such cases, a third blinded reviewer will review the scores given from each of the two primary independent reviewers and determine which score is more accurate, that of reviewer A or reviewer B (adjudication by consensus). The adjudicator's decision will be the final score for that video assessment.

The statistical analysis of this endpoint will utilize a single sample t-test comparing the mean value of the primary endpoint with zero. This endpoint allows the effect N-Acetyl-L-Leucine to be measured both in terms of improvement during treatment followed by any deterioration once treatment is removed.

Summary statistics will in addition be calculated separately according to subgroups defined by the primary anchor test

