8.5.1 Primary Efficacy Endpoint

The primary endpoint is based on the modified 5-domain NPC-CSS score with success defined as no change or a decrease in the 5-domain NPC-CSS score from Visit 7 to Visit 9.

It is postulated that under standard of care, 90% of patients would worsen (higher score) in terms of their performance in 5-domain NPCS-CSS scale over a 12-month period, while conversely only 10% would show similar performance or some improvement. Statistical evaluation of the primary binary endpoint (success/failure on the 5-Domain

NPC-CSS scale) will compare the proportion of success with 10% in a one-sided Fishers Exact test at the one-sided 5% significance level.

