14.2.24	Frequency table of the CI-CS score for the non-primary anchor test Visit 4 vs Visit 2 and separately, the CI-CS score Visit 6 vs Visit 4 according to subgroups (mITT population)
14.2.25	Descriptive statistics of the CI-CS score for the non-primary anchor test Visit 4 vs Visit 2 and separately, the CI-CS score Visit 6 vs Visit 4 according to subgroups (mITT population)
14.2.26	Result of t-test or Wilcoxon test on the change in SARA total score between Visit 2 and Visit 4, as well as Visit 4 and Visit 6 (mITT and PPS population)
14.2.27	Descriptive statistics of the SARA total score and 8 subscores at each visit (mITT and PPS population)
14.2.28	Mean or median plot versus time of the SARA total score (mITT and PPS population)
14.2.29	Stacked bar chart of the 8 SARA subscores at each visit (mITT and PPS population)
14.2.30	Spaghetti plot of SARA total score at each visit (mITT and PPS population)
14.2.31	Descriptive statistics of the SARA total score and 8 subscores at each visit according to subgroups (mITT population)
14.2.32	Result of t-test or Wilcoxon test on the change in SCAFI total score, and subscores 8MW_avg, 9HPT-D_avg and PATA_avg between Visit 2 and Visit 4, as well as Visit 4 and Visit 6 (mITT and PPS population)
14.2.33	Descriptive statistics of the SCAFI total score and subscores 8MW_avg, 9HPT-D_avg, 9HPT-ND_avg and PATA_avg at each visit (mITT and PPS population)

14.2.34	Mean or median plot of SCAFI total score versus time (mITT and PPS population)
14.2.35	Spaghetti plot of SCAFI total score versus time (mITT and PPS population)
14.2.36	Descriptive statistics of the SCAFI total score and subscores 8MW_avg, 9HPT-D_avg, 9HPT-ND_avg and PATA_avg at each visit according to subgroups (mITT population)
14.2.37	Frequency table of the EQ-5D-5L and EQ-5D-Y health status and 5 subdomains at each visit (mITT and PPS population)
14.2.38	Frequency table of the EQ-5D-5L and EQ-5D-Y health status and 5 subdomains at each visit according to subgroups (mITT population)
14.2.39	Descriptive statistics of the EQ-VAS for -5L and -Y combined at each visit (mITT and PPS population)
14.2.40	Mean or median plot of EQ-VAS versus time for -5L and -Y combined (mITT and PPS population)
14.2.41	Spaghetti plot of EQ-VAS versus time for -5L and -Y combined (mITT and PPS population)
14.2.42	Descriptive statistics of the EQ-VAS for -5L and -Y combined at each visit according to subgroups (mITT population)

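### SARA, SCAFI and three SCAFI subtests are tested only as separate single-period changes; the trend-cancelling contrast used for the primary endpoint is missing for them

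*SAP*

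**What the plan says.** SAP 5.6.3 (Measurement of Ataxia and Functioning) names five tested measures and the first period: "The changes in SARA total score, SCAFI total score, the SCAFI subscores (8MW_avg, 9HPT-D_avg, and PATA_avg) between Visit 2 and Visit 4". It continues with the second period: "as well as the changes between Visit 4 and Visit 6 will be analysed using a one-sample t-test or a Wilcoxon Signed Rank test". The non-dominant hand is left out of testing: "The SCAFI subscore 9HPT-ND_avg will only be descriptively summarized in tabular format".

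SAP 4.1.3 defines all additional secondary endpoints as these two changes. The planned output follows suit. Table 14.2.26 is the "Result of t-test or Wilcoxon test on the change in SARA total score between Visit 2 and Visit 4", together with the Visit 4 to 6 change, and Table 14.2.32 does the same for SCAFI. Protocol 8.5.2 lists the two changes under descriptive statistics. For the tests it says only that these scores get a single-sample t-test or Wilcoxon test.

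Other endpoints are handled differently. For the primary endpoint, SAP 5.6.1 says: "The primary statistical analysis will be performed using a one-sample t-test comparing the CI-CS difference score to zero". SAP 5.6.2 applies the same construction to the averaged CI-S. Within 5.6.3 itself, for the physician rating, "the CGI-C from Visit 2 to Visit 4 minus the CGI-C from Visit 4 to Visit 6 will be compared to a difference of zero". Table 14.2.58 shows that the physician CGI-C also keeps single-period tests beside the difference.

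SAP 5.1 uses one-sided p < 0.05, treats it as only indicative outside the primary endpoint, calls all non-primary evaluations exploratory, and makes no multiplicity adjustment.

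**The concern.** All patients receive the drug. A change tested against zero therefore speaks for the drug only if the expected change without the drug is zero. Two ordinary mechanisms break that condition. Decline in a progressive disease produces worsening from Visit 4 to Visit 6 whether or not a drug was withdrawn. Practice on timed tasks repeated at every visit produces improvement from Visit 2 to Visit 4.

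The plan's primary endpoint is built to deal with this. Protocol 8.5.1 explains its purpose: "This endpoint allows the effect N-Acetyl-L-Leucine to be measured both in terms of improvement during treatment followed by any deterioration once treatment is removed". Subtracting the second change from the first removes any trend that is equal in both periods. For the primary endpoint the two single-period components are only described (SAP 5.6.2). For the ataxia scales those components are the only tests.

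At stake is what these scales can support. They are the formally tested ataxia scales under the secondary objective on ataxia symptoms and functioning. As planned, their p-values do not address the same quantity as the primary endpoint, and one of each pair can fall below 0.05 for reasons unrelated to the drug.

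**Working it through.** **1. The plan's own figure.** The only power figure is for the parent study's primary endpoint (SAP 2.4.1): n = 30, mean 0.45, SD 1.02, one-sided 5%. Effect size 0.45/1.02 = 0.441; noncentrality 0.441 × √30 = 2.416; critical t on 29 df = 1.699. Power = 76.3%, against the stated 76%, so it reproduces. The documents give no power, SD or drift for SARA or SCAFI.

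**2. Inputs for the check.** About 36 patients in the mITT and about 30 per protocol (Protocol 3.1.3). Drift per period, k, in SDs of a single-period change, is an assumption: 0.1, 0.2 and 0.3. The SAP does not state the direction of the one-sided tests; improvement for Visit 2 to 4 and worsening for Visit 4 to 6 are assumed. Visit errors are independent normal with variance σ², scaled so that a single-period change has SD √2·σ = 1. The drug effect is zero.

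**3. Single-period tests.** Rejection probability = 1 − F(t; n−1, k√n), where F is the noncentral t distribution function and t the one-sided 5% critical value (1.690 at n = 36, 1.699 at n = 30). For the period that drift works against, k is replaced by −k.

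| n | k | test favoured by drift | other test |
|---|---|---|---|
| 36 | 0.1 | 14.5% | 1.3% |
| 36 | 0.2 | 32.0% | 0.24% |
| 36 | 0.3 | 54.8% | 0.03% |
| 30 | 0.1 | 13.4% | 1.5% |
| 30 | 0.2 | 28.3% | 0.33% |
| 30 | 0.3 | 48.4% | 0.06% |

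Under decline, the favoured test is Visit 4 to 6; under practice gain it is Visit 2 to 4. Simulation (50,000 trials per setting, n = 36) puts both tests positive together at 1.2% with no drift, and at 0.7%, 0.2% and 0.04% at k = 0.1, 0.2 and 0.3 of practice gain. Joint positivity is not inflated.

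**4. Difference of changes.** D = (V4−V2) − (V6−V4) = 2·V4 − V2 − V6. Under equal drift its expectation is k − k = 0. Simulated rejection was 4.9% to 5.1% at every steady drift tried, up to k = 0.5, at both sample sizes.

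**5. Where the contrast does not protect.** Var(D) = 6σ² = 3 on the scale used, so its SD is √3.
- Practice gain that stops after Visit 4: the mean of D is k and the effect size k/√3. At n = 36 this gives 16.7% at k = 0.2 and 26.6% at k = 0.3, still well below 32.0% and 54.8%.
- A bias that lifts Visit 4 only: the mean of D is 2k and the effect size 2k/√3. At n = 36 this gives 38.7% and 65.3%, somewhat worse than the single-period 32.0% and 54.8%.

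**6. Sensitivity to a real effect.** With effect δ, of which a fraction r is lost by Visit 6, the signal-to-noise of D is (1+r)δ/(√6·σ), against δ/(√2·σ) for the Visit 2 to 4 change. At r = 1 the multiples of δ/σ are 0.82 and 0.71. At r = 0 they are 0.41 and 0.71. They are equal at r = √3 − 1 = 0.73.

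**The case against.** The other side has a good case on several points.

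- **Rank.** The SAP treats these p-values as indicative and exploratory, and SAP Section 7 ties trial success to the parent study's primary endpoint alone. This stands and limits the consequence.
- **Visibility.** Both periods appear in the same tables, with plots over time for the SARA and SCAFI totals. Steady decline suppresses the Visit 2 to 4 test, so an isolated washout worsening would show. This stands in part: a careful reader would see it, but nothing in the plan requires both periods to agree before a result is called indicative.
- **Drift size.** No document gives one. A reader might infer that the plan itself assumes decline on these scales, since Protocol Appendix 6 (8.5.1) postulates that 90% worsen under standard of care. That figure concerns the 5-domain NPC-CSS over 12 months and is a proportion. It supports the direction of decline, not a six-week drift in SARA or SCAFI.
- **Replacing the tests.** A reader might conclude that the single-period tests should be reduced to description. The documents do not compel that. The protocol lists the two changes, the physician CGI-C keeps single-period tests beside its difference, and the contrast is less sensitive if benefit persists. The sponsor cites evidence of slowed progression, so separate periods are defensible.
- **Rater expectancy.** Site staff score SARA and SCAFI in an unblinded study, so it would be wrong to call them objective. If expectancy lifts Visit 4 only, the contrast is no remedy and does slightly worse.

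None of this supplies a reason to omit the contrast.

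**Conclusion.** The point holds as an omission with a cheap remedy. For five measures the plan tests two single-period changes against zero and lacks the contrast on which it relies elsewhere. Under steady drift of 0.1 to 0.3 SD per period and no drug effect, one of each pair of tests rejects in 14.5% to 54.8% of trials at n = 36, or 13.4% to 48.4% at n = 30. The lower sample size may be closer for Visit 4 to 6, because the mITT does not require Visit 6 data and these endpoints are not imputed. The rates rest on assumed drift, independent normal visit errors and the assumed test directions.

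Two stronger readings should be resisted. One is that the ataxia results as a whole are inflated: each kind of drift raises one test and lowers the other, and the two together are not inflated. The other is that the trial's conclusion is at risk: success rests on the primary endpoint, which already uses the difference. What changes is how much weight an isolated p-value on these scales can bear.

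**What to change.** In SAP 5.6.3, add the per-patient (V4−V2)−(V6−V4) for SARA total, SCAFI total, 8MW_avg, 9HPT-D_avg and PATA_avg. Test it against 0 (t-test or Wilcoxon, as now) with a two-sided 90% CI, and name it the main inferential contrast for these measures. State the direction of benefit for each, since lower is better for SARA and the timed tests and higher is better for SCAFI and PATA. Report it beside the existing single-period results in Tables 14.2.26 and 14.2.32, and state that a single-period p < 0.05 alone is not evidence of drug effect. Update SAP 4.1.3 and record the addition in SAP Section 7.

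The SAP should also state the limits:
- The contrast cancels only drift that is equal in both periods. Plateauing practice leaves inflation, and postponed Visits 4 or 6 can make the periods unequal.
- It does not remove expectancy of unblinded raters at Visit 4.
- It loses power if benefit persists through washout.
- Patients without a Visit 6 value do not contribute; they are already absent from the Visit 4 to 6 test.

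The cost is SAP text, two tables and five further unadjusted p-values, which is why one contrast should be named as the main one. No new data are needed, and the protocol's listed changes stay in place.

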5.6.4 Other additional statistical analyses

The following analysis will provide an estimate of intra-patient variability and provides information on the stability of the outcome evaluation. Note that, considering the high degree of variability within and between these patients, this is only a simple approach as results may be influenced by e.g. rater variability, disease progression or treatment effect.

The analysis will be done for the mITT population only, and only for the CI-S outcome of the videos. No sensitivity analysis will be applied, and no separate analysis will be performed for subgroups.

The Intraclass Correlation Coefficient (ICC) will be used as an index of reliability to measure agreement between pairs of observations for Visit 1 and 2, Visit 3 and 4, and Visit 5 and 6 respectively, presenting the proportion of the total variance in the observations that is due to the differences between pairs. The ICC takes on values between 0 (meaning no agreement) to 1 (perfect agreement), with an ICC >0.80 representing high reliability. No imputation for missing visits will be done, and the ICC can only be determined for subjects having data for both visits in the pairs. The ICC value and the corresponding 95% confidence interval will be presented in a tabular format, and for additional clarity the number of available pairs will be added as well.

